## We will recruit 60 IPS clients from the RCT and 20 Thresholds staff, managers, and leaders into the implementation evaluation of VR. *Inclusion/exclusion criteria are outlined below:*

Inclusion Criteria: 1) participated in RCT (IPS clients only); 2) employed by Thresholds as an Employment Specialist, Team Leader, or IPS Manager; or 3) employed by Thresholds at the level of Director or higher.

Exclusion Criteria: None.

#### 4.0 Procedures Involved:

### A. Study Settings

This study will collect human subjects data at several approved locations throughout the city of Chicago. First, subjects will be enrolled and evaluated by research team members at an approved Thresholds location (see Appendix A). Then subjects will travel to either the Northwestern University Feinberg School of Medicine (NU) campus Department of Psychiatry and Behavioral Sciences' clinical research program ([name]) or an approved Thresholds site where the NU and Thresholds research teams will collect additional human subjects data. The decision on the location will be flexible due to scheduling of participant, actor, and staff availability. Subjects who are randomized to the VR training will complete the training at either NU or one of the approved Thresholds locations.

### **B. Study Design**

This is a two arm randomized, single blinded, intent-to-treat, controlled trial (RCT) with baseline and pre-test assessments, up to 10 hours of VR training, post-test assessment, and follow-up at 6 months and at 9 months. We will evaluate both person-level and system-level outcomes associated with implementing VR at Thresholds. At the person-level, we propose to evaluate if IPS+VR, as compared to IPS Only, is associated with better employment outcomes (higher employment rate, shorter time-to-employment), job interviewing skills, and greater reductions in psychological distress. Interviewing anxiety and self-efficacy will be explored as potential mechanisms in the pathway between IPS and employment. At the system-level, we propose to conduct a cost-effectiveness analysis and budget impact analysis between IPS+VR and IPS Only as well as explore whether Employment Specialists (Thresholds Staff that work one-on-one with clients) working at Thresholds spending fewer hours leading interview training is related to spending more hours completing job applications with clients and building a network of employers. We will also explore if VR generalizes to social skills at both the person-level (via job retention measures) and the system-level (using a time log completed by Employment Specialists regarding time spent coaching communication skills at work).

### C. Study Intervention

SIMmersion, LLC designed VR to enhance job interview skills for adults with SMI. The job-related interview

content objectives target: 1) conveying oneself as dependable, 2) negotiating skills (e.g., asking for a day off), 3) team work, and 4) honesty (e.g., following company policy). The Interviewee performance objectives target: 1) comfort level during the interview, 2) sharing information in a positive way, 3) sounding interested in the position, 4) sounding professional, and 5) establishing a rapport with the interviewer. SIMmersion designed VR with the following components to help learning:

C.1.a Electronic Learning (e-learning): Interactive e-learning screens (Figure A.) display critical information needed to prepare for a job interview such as creating a resume, researching a position, types of questions to ask, advice on how to disclose a disability, and an emphasis on effective skills for interacting with the interviewer (e.g., dealing with emotionally provocative questions).

C.1.b VR Interface and "Molly Porter": After using the e-learning module, trainees will navigate the program to begin the simulated interviews with a virtual human resource staff at a department store named "Molly Porter." She is sitting in her office and the trainee has joined her for an interview. When "Molly" speaks, the program enters Full Screen mode (Figure B) so that she is speaking directly to the trainee without any distractions on screen. When she finishes asking her question, the program returns to the interface in Figure C where trainees speak a prescripted response of their choosing (see C.1.d).

"Molly" has three difficulty levels: easy (e.g., friendly), medium (e.g., direct), and hard (e.g., stern or asks illegal questions). She uses "memory" and her behavior is driven by an advanced "emotional model." For

example, if a trainee responds inappropriately to several questions, "Molly" may become dismissive and end the interview, but if the trainee continually answers appropriately, "Molly" may become more friendly and encouraging. Based on the trainee's statement, the software must then choose a reply for "Molly." Selection is based on three factors: 1) difficulty, 2) the history of the conversation, and 3) "Molly's" evolving relationship with the trainee, driven by trainee responses. Each factor will be used to compute conditional probabilities associated with each possible reply and one is selected. "Molly" stays true to her character and the emotional state created during the play, and thus, may behave differently each time the system is used.

Figure C displays the layout of the interview interface. Buttons at the top of the screen control the interface. The yellow text displays various statements that can be spoken to respond to "Molly's" questions. The interview transcript can be accessed through a tab in the middle of the

screen. The trainee may change the topic during the conversation using buttons to the left of the yellow text. An on-screen coach appears in the bottom right of the interface. The trainees can take notes and review prior questions (white and gray boxes).

C.1.c Video Clips: A professional actor portrayed "Molly" during the video-recorded sessions. The videos were separated into >1,000 question and response clips that are played during the simulated interview. Trainees talk with "Molly" using a microphone and voice recognition software. This method exposes trainees to an interactive environment and helps them learn to react to an interviewer's social cues.

C.1.d Pre-scripted Statements and Voice Recognition: A panel of vocational experts supervised hundreds of responses to standard interview questions written by professional scriptwriters during the initial SBIR grant award. The scriptwriters worked with the scientific team to compose realistic dialogue that provides trainees with opportunities to practice the skills identified in the learning objectives. Trainee statements included a wide variety of natural choices with 5-15 potential responses that vary in appropriateness of their content. This method allows trainees to choose and learn from their responses. VR uses voice recognition technology so trainees can practice speaking the pre-scripted responses to difficult questions in a stress-free environment. Then, trainees can use the rehearsed answers in real interviews.

C.1.e Non-branching Logic: SIMmersion's PeopleSIMTM technology uses non-branching logic; which allows trainees to behave and speak freely within the confines of a safe simulation. Most social simulations, in contrast, use branching logic where trainees select a response from a list of options, which terminate when all options are exhausted. This approach minimizes repeated use to a few trials. SIMmersion's technology integrates the video clips and non-branching logic to enable "Molly" to vary her memory, emotion, and personality. This variation supports hours of unique repeated practice and naturalistic conversations with Molly.

C.1.f Job Coach and Help Buttons: Trainees receive in-the-moment feedback from an on-screen coach (Figure D.) who provides nonverbal cues regarding the trainee's choice of questions and statements. If further clarification is needed, the trainee can click "help" buttons that provide additional detail to clarify the interview question or the trainee's response statement. For example, the coach gives the trainee a "thumbs down" sign if an inappropriate response is selected (Figure D.). If the trainee is unclear about the negative feedback, he or she can click the help button to get a more detailed written and verbal explanation about why the statement was inappropriate (e.g., "This statement focuses on a negative character trait; try focusing on your strengths").

C.1.g Individualized Customization: Prior to starting VR interviews, trainees complete an online job application, which includes questions about employment history and work skills. Trainees will specify one of eight different jobs (cashier, stock clerk, customer service, maintenance/grounds, janitorial, food service, inventory, or security). This "on-line" application procedure is based on applications currently in use by employers such as Target and Home Depot. This practice prepares trainees to accurately complete online applications. Additionally, the application data will populate the list of questions from which "Molly" will draw. For example, a trainee may apply for a customer service position on the application, yet identify previous experience in inventory; Molly may ask, "I see from your resume that you have experience in inventory and are applying for a customer service position. Why are you looking to make that change?" This innovative feature allows trainees to customize their interview experiences to better prepare themselves for future interviews.

C.1.h VR Transcripts: During or after the interview, trainees can view a transcript that replays individual exchanges or the entire conversation. If trainees are using the speech recognition feature, the transcript will also replay his or her recorded voice. This feature lets the trainee hear (and reflect upon) the tone of voice used to ask questions and make statements. The transcripts are color coded to reflect

helpful, unhelpful, and neutral responses. Participants can click on the response to receive detailed information about why a response was helpful for hurtful to their job interview and learn how "Molly" understood their responses.

C.1.i Scoring and Summary Feedback: After each virtual interview, trainees receive scores in eight categories (based on the learning objectives). The scores are scaled from 0-100 and are computed via an algorithm, which accounts for the types of responses provided by the trainee throughout the course of the interview. Participants view this scoring feedback and if they score 80 or higher they are informed, "You got the job! You made a great impression on "Molly" and she decided to offer you the job. Congratulations!" (See VR Training Manual in Supporting Documents for Screen Shots). Trainees also receive feedback summaries of what they did well and where they need improvement. This feedback helps trainees understand the subtleties of their interview skills.

### D. Study Procedures for Community Effectiveness Randomized Controlled Trial

D. 1.a. Thresholds research staff will prescreen members using Electronic Health Record (EHR) information. Thresholds research staff will sit in on weekly case coordination visits with Employment Specialist (ES) to discuss members who may be a good fit for the study. If the member agrees, the ES will talk directly with the member to explain the study and see if he/she is interested. The ES may use a recruitment video at this time. Once interest is established, Thresholds research staff will reach out to the client directly via phone. The Thresholds research staff member will use the study screening form to determine the client's initial eligibility for study participation, and then schedule a baseline visit. Screening data collected from individuals who are ineligible or decline participation will be kept on file during the duration of the recruitment period in case eligibility criteria changes then this information will be destroyed after recruitment is completed.

D.1.b. The Thresholds Employment Specialist identifies members who are eligible for research participation base on member's enrollment and employment status. The Employment Specialist give members' information about the research study using the kickoff meeting recruitment script and kickoff meeting recruitment handout, and lets the member know that they may be eligible for the study. The Employment Specialist asks members if they would be interested in learning more about the study at a kickoff meeting with the research team. The kickoff meeting will be a two-hour period at a Thresholds location in which the interested member will have the option to talk to the Thresholds research team. The member will also have the option to talk to the Thresholds' research team via phone instead of attending the kickoff meeting. The Thresholds research team may use the Molly information video during the kickoff meeting. Once interest has been established in joining the study, the Thresholds research staff member will use the study screening form to determine the client's initial eligibility for the study participation, and then schedule a baseline visit. Screening data collected from the individuals who are ineligible or decline participation will be kept on file during the duration of the recruitment period in case eligibility criteria changes. Then this information will be destroyed after recruitment is complete.

D. 2. The Baseline Visit for Thresholds' Clients (completed at Thresholds) will begin with Wide Range Achievement Test (4th Edition) to assess current reading level (lasting approximately 10 minutes). If the client is found eligible based on reading level (6th grade or above), they will complete the informed consent process and provide contact information (lasting approximately 20 minutes). Thereafter, research staff will administer:

1. Structured Clinical Interview for DSM-V Axis I Disorders (SCID-5) (lasting approximately 1 hour) . The SCID will provide duration of illness, number of psychiatric hospitalizations, current medication status, and educational attainment. A medication log will be used to capture the medication information.

In the SCID, if a patient endorses any items regarding suicidality (item OP8, "Suicidal ideation lifetime" [if within last 30 days], item OP9, "Suicidal ideation past week," item OP13, "Suicide attempt lifetime"

[if within last 30 days], or item OP14, "Suicide attempt past week"), research personnel will administer the **Columbia-Suicide Severity Rating Scale (C-SSRS)**. A total score of 4 or higher on the "Intensity of Ideation" section of this measure will indicate whether or not the participant has a level of suicidal risk that requires further consideration. Example questions from the C-SSRS are listed below),

Preparatory Acts or Behavior:	Yes	No
Acts or preparation towards imminently making a suicide attempt. This can include		
anything beyond a verbalization or thought, such as assembling a specific method		
(e.g., buying pills, purchasing a gun) or preparing for one's death by suicide (e.g.,		
giving things away, writing a suicide note).		

Have you taken any steps towards making a suicide attempt or preparing to kill yourself (such as collecting pills, getting a gun, giving valuables away or writing a suicide note)? If yes, describe:

The procedures outlined in section 10 (Risks to Participants) will be followed if a participant scores 4 or higher.

2. Participants will receive a 5 minute break.

3. Alcohol Use Disorders Identification Test Self Report (AUDIT-SR) (lasting approximately 5-10 minutes). The AUDIT-SR will provide self-reported alcohol use information.

4. Drug Abuse Screening Test 10 item (DAST-10) (lasting approximately 5-10 minutes). The DAST-10 will provide self-reported drug use information.

5. Job Interview Self-Efficacy is a 9-item self-report (approximately <5 minutes)

6. Personal Report of Job Interview Anxiety is a 34 item self-report to assess one's level of anxiety regarding the job interview process (approximately 2 minutes)

7. Intrinsic Motivation Inventory – Employment Research is a 30 item self-report (approximately 10 minutes)

8. Technology Comfort Level Questionnaire is a 6-item measure that assesses one's comfort level with computer technology (approximately 5 minutes).

9. Research staff will complete the inclusion / exclusion checklist. If participant is eligible to proceed, they will be scheduled to return to Thresholds for Baseline Visit 2/3.

The Baseline Visit 1 will last approximately 210 minutes or 3 hours and 30 minutes. Participants will be paid \$70. This amount will be prorated on the number of assessments completed if the session ends early. For example, if a participant is excluded based on reading level, he or she will be paid \$15.

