### **10.0 Risks to Participants:**

Potential Risks and Protections in Place Against Foreseeable Risks. The potential risks of this project are minimal. The possibility exists that participants may become bored or fatigued during: 1) pre-test and post-test role-plays; 2) VR training; 3) cognitive assessments; 4) vocational history interview; or 5) mental health history

interview. In response, we will include scheduled and unscheduled breaks to protect against these risks. To minimize the risk of possible fatigue and/or boredom, breaks will be scheduled between assessments in long sessions and between role-plays, and participants will be reminded that they can request a break at any time during. Should a research staff member notice signs of fatigue and/or boredom from a participant, an unscheduled break will be taken. The research team has used these procedures for other studies, and they have been effective at reducing risks of fatigue and/or boredom for study participants.

There is a very low risk that participants could be distressed by the mental health interview or job interview role plays. If this happens, participants will be asked to take a break and be offered the chance to drop out of the study if these aspects of the study are too distressing for them. Of the more than 150 participants who completed the mental health interview and four role-plays each during the efficacy studies (600 total role-plays), no participants reported feeling distressed by the interview or role-plays.

These risks will be reviewed during the discussion regarding informed consent, and researchers will take all possible precautions to minimize these potential risks. Moreover, only personnel trained in interviewing and testing protocols with individuals 18 year and older will conduct these procedures.

Although there are no known adverse or severe adverse events that have occurred as a result of using the training, it is possible that a participant could arrive to a research visit (or escalate during a research visit) in a way that is symptomatic or suicidal during the course of the study. Per Thresholds and NU policies, both sites will have clinical staff available (including the PI, [name]) to assess the mental health and the risk of harm to self or others. If trained research staff observe a participant to be highly symptomatic or suicidal then they will follow the following policies at NU and Thresholds:

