# If suicidal ideation is detected (based on Beck Depression Inventory item 9 cut-off score of 2 or 3, OR other indication):

- Administer the Columbia Suicide Severity Rating Scale (C-SSRS). If participant scores 4 or higher on the "intensity of Ideation" section, proceed with emergency procedures.
  - If participant scores below 4, continue with study procedures per protocol and notify primary Thresholds research staff point of contact (i.e., [name], [name]) of C-SSRS outcome. Threshold's research staff should follow up with participant's clinical team.

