### Emergency procedures

- NU staff should alert the Research Manager and primary Thresholds research contact about the concern (provide with demographics and relevant medical information such as suicidal and/or homicidal ideation/intent, diagnosis, medical condition).
- Thresholds research staff should contact participant's clinical team and obtain recommended next steps (i.e. go immediately to ED, wait for clinical staff to arrive, or schedule an appointment for the participant with clinical provider).
- Pending recommendation from Thresholds clinical provider (if recommended to make appointment with provider or go immediately to Emergency Department), discuss the issue with all relevant research staff and participant.
- If recommended to make appointment with provider, ensure that appointment is secure promptly and that date, time, location, and name of provider appointment are documented before participant leaves the research premises.
- If recommended to go immediately to ED:
  - Call 911.
  - In the case of an involuntary hospitalization/ED evaluation: call Police; a research team member should go with police since "Petition" is required.
  - In the case of a voluntary hospitalization/ED evaluation: call Ambulance to escort thepatient.
  - In the case of suicidal ideation/intent, a research team member must watch (i.e., must have eyes on) the participant until Police/Security/Ambulance arrives.

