### Withdrawal of Participants

The above noted cases regarding suicidality and symptom exacerbation are the anticipated situations when the participant will be withdrawn without their consent.

Participants withdrawn from research will:

- not be called to participate in future research visits for the current study;
- have their data included in all analyses unless there is a formal, written request by the participant to have their data removed from analyses (as noted in the consent form).

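### Emergency procedures start only on a C-SSRS Intensity of Ideation score of 4 or higher, so a suicide attempt in the last 30 days reported at Visit 1 does not by itself require a clinical decision before the person leaves

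*Combined protocol and SAP*

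**What the plan says.** **Triggers for the C-SSRS.** Section 4.0 D.2 and the SCID part of section 10.0 give the C-SSRS at Visit 1 to anyone endorsing one of four SCID items: OP8 or OP9 (ideation), or OP13 or OP14 (attempt), with OP8 and OP13 limited to the last 30 days. At Visit 2/3 (D.3) and Visits 10 and 11 (D.6, D.8) the listed trigger is BDI item 9 rated 2 or 3.

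**Action threshold.** D.2 and D.3 use the same one: "A total score of 4 or higher on the 'Intensity of Ideation' section". Section 10.0 repeats it as the step into the emergency branch: "If participant scores 4 or higher on the 'intensity of Ideation' section, proceed with emergency procedures".

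**Below the threshold.** "If participant scores below 4, continue with study procedures per protocol and notify primary Thresholds research staff point of contact". Thresholds research staff are then to follow up with the clinical team. No time is given.

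**Inside the emergency branch.** "Thresholds research staff should contact participant's clinical team and obtain recommended next steps". The listed possibilities are going to the emergency department, waiting for clinical staff, or an appointment. Appointment details must be "documented before participant leaves the research premises".

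**Eligibility.** Exclusion 4 (section 3.0) uses a score of 4 or 5 on the C-SSRS Suicidal Ideation section, which is not the Intensity section. Exclusion 5 is an attempt in the past 30 days. The inclusion/exclusion checklist is the last step of Visit 1.

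**Withdrawal.** Section 10.0 states: "The above noted cases regarding suicidality and symptom exacerbation are the anticipated situations when the participant will be withdrawn without their consent". Those withdrawn will "not be called to participate in future research visits for the current study".

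**The concern.** The protocol treats a recent attempt, and ideation with some intent to act, as serious enough to keep a person out of the trial. Neither finding reaches the branch that obtains a clinician's recommendation. Entry to that branch depends on a different section of the C-SSRS, one that scores ideation.

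Two people who report the same attempt last week can therefore be handled differently. One scores 4 on Intensity, and the clinical team must say what happens next. The other scores below 4, staff carry on with the visit, and the handover to the clinical team has no deadline. The second person is also excluded by the Visit 1 checklist, so no later study visit would pick them up.

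Participant safety is at stake here. The sample size, the type I error rate and the treatment comparison are not affected.

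**Working it through.** There is no figure to reproduce. The check follows each suicidality finding through the text to the action it requires.

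| Finding | Where it can arise | Stated consequence | Starts the emergency procedures by itself? | Makes the person ineligible? |
|---|---|---|---|---|
| Intensity of Ideation 4 or higher | Any C-SSRS | Emergency procedures | Yes | Not named in 3.0 |
| Suicidal Ideation 4 or 5 | Any C-SSRS | None stated for escalation | No | Exclusion 4 |
| Attempt in last 30 days (OP13, OP14) | SCID, Visit 1 | C-SSRS | No | Exclusion 5 |
| Preparatory acts | C-SSRS question printed in D.2 | None stated | No | Not by itself |
| Recent ideation (OP8, OP9) | SCID, Visit 1 | C-SSRS | No | Only if exclusion 4 is met |
| BDI item 9 rated 2 or 3 | Visits 2/3, 10, 11 | C-SSRS | No | Only if exclusion 4 is met |
| Distress during procedures | Any visit | BPRS and/or C-SSRS; no BPRS cut-off given | No | No |
| Staff observe a highly symptomatic or suicidal participant | Any visit | The section 10.0 steps above | Not stated; those steps use the same score | No |

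Counts from these rows:

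- Of the 4 SCID triggers, 2 are attempt items (OP13, OP14). The emergency rule contains 0 attempt or behavior items.
- Scheduled visits with a C-SSRS trigger are 1, 2/3, 10 and 11, which makes 4. Attempt items are a listed trigger at 1 of them (Visit 1). The other 3 list only BDI item 9, which asks about ideation.

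**A recent attempt at Visit 1.** OP13 or OP14 leads to the C-SSRS. With Intensity at 4 or higher, the clinical team is contacted and recommends a course. The steps that follow (escort, observation, or an appointment fixed before departure) all fall within the visit. With Intensity below 4, the visit continues, the research contact is told, and the clinical team is followed up at an unspecified time. The attempt answer does not alter which branch applies.

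**Before randomization.** At Visit 2/3 every participant completes the BDI. Item 9 rated 2 or 3 leads to the C-SSRS, Intensity 4 or higher leads to section 10.0, and the withdrawal paragraph anticipates removal. D.4 then opens the envelope. So an ideation screen does precede randomization. Neither D.3 nor D.4 mentions a second look at attempts, a repeat checklist, or use of the Suicidal Ideation section that defines exclusion 4.

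**The case against.** The strongest reply is that safeguards outside the score exist. Section 10.0 says "both sites will have clinical staff available" to assess mental health and risk of harm, under Thresholds and NU policies that are not reproduced. It also covers a participant whom staff simply observe to be suicidal. Visit 1 takes place at Thresholds, the participant's own service provider. Below 4, the research contact must still be told the result and the clinical team must still be followed up. All of this stands: the handover exists and lacks a deadline. It does not remove the point, because the observation clause sends staff to the listed steps, and the distress and other-indication routes lead back to the same score. Clinical judgment is possible at each step, but the text does not require it.

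A second reply is that the affected group may be very small. Whether a total of 4 is a high or a low bar depends on C-SSRS scoring rules that the documents do not give. This also stands, and no frequency is claimed here.

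A third reply is that one eligibility check, followed by an ideation screen before randomization, is a defensible design for job-interview training whose risks the protocol calls minimal. Any missed case would be randomized like everyone else, so no bias between arms follows. Section 14.0 also refers to eligibility forms and audits that are not shown. For these reasons the Visit 2/3 point is minor and limited to what is not described.

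**Conclusion.** The escalation gap is real on the text and should be closed. A recent attempt, a positive preparatory-acts answer, or a Suicidal Ideation score of 4 or 5 does not by itself start the emergency procedures. Below 4 on Intensity, no clinical decision is required before the person leaves. This rests on reading section 10.0 as written and on the institutional policies it mentions adding no same-visit rule. The number of people affected cannot be derived.

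A reader might infer more than the documents support:

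- *That a recent attempter is left without clinical follow-up.* The below-4 branch requires it, though without a time limit.
- *That a recent attempter found at Visit 1 would be randomized.* The Visit 1 checklist applies exclusion 5.
- *That people reach randomization with no suicidality screen after Visit 1.* BDI item 9 and the C-SSRS come first. What is not described is a repeat question about attempts, or re-application of exclusions 4 and 5.
- *That the exposure can be sized from the time between Visit 1 and Visit 2/3.* The interval is not stated, and it would say nothing about how many people are affected.

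**What to change.** **Escalation (D.2, D.3 and the C-SSRS step in section 10.0).** Replace the single threshold with:

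*Start the emergency procedures, contacting the clinical team and obtaining its recommended next steps before the participant leaves, if any of these is present: (a) an Intensity of Ideation score of 4 or higher; (b) a Suicidal Ideation score of 4 or 5 in the last 30 days; (c) a suicide attempt, or preparatory acts or behavior, in the last 30 days.*

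Begin the below-4 bullet with *If none of (a) to (c) is present*, and require contact with the clinical team the same day.

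**Withdrawal.** State that after randomization the added triggers (b) and (c) do not by themselves withdraw a participant. Leave the present rule for (a) unchanged, since nothing here justifies reversing it. Without this sentence, a wider emergency branch could end follow-up for more people. The power calculation for Hypothesis 1 allows 10% missing of 2 × 80 = 160, or 16 participants. Each extra 1% withdrawn is 0.01 × 160 = 1.6 participants, and 1.6/16 = 10% of that allowance.

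**Optional (D.3 or D.4).** Re-ask OP13 and OP14 at Visit 2/3 before the envelope is opened. That is 2 questions per participant: 2 × 160 = 320 for the analysis plan's 160, or 2 × 180 = 360 for the 180 in section 3.0.

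**Cost.** Amendment wording, a staff briefing, and a few more same-visit contacts with the clinical team. If the optional step is taken, a few more people might be excluded before randomization and need replacing.
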